#### 10B. Expected Attrition and Power Analysis

**Attrition.** Our target population is pretrial detainees who are returning to the community. We will exclude individuals who expect to be sentenced to prison. However, we expect 6-8% of the pretrial jail detainee participants we consent who do *not* expect to be sentenced to prison will be sentenced anyway. These individuals will not leave jail for the community (i.e., will go

directly to prison, not home), meaning that they are not actually eligible for the study, which is a study of suicide prevention in the year after release from pretrial jail detention. Therefore. individuals who go to prison directly from jail rather than back to the community will not be followed, and have been included in our study attrition estimates. This is a standard approach taken in other re-entry studies (e.g., R01 AA021732; U01 DA01619113) that must consent participants when their sentencing or release status is still unknown. Sentencing will occur independent of study condition, so their exclusion from analysis (no "at-risk" community months) will be unlikely to influence internal validity. We will follow all remaining participants who are released from jail to the community after the index incarceration through the 52-week postrelease period regardless of reincarceration, continued participation in SPI or SOC, or subsequent suicide attempts or hospitalizations. For randomized participants who are not released from jail by the assessment window closing date (see Section 10A), the study PIs can decide to terminate the participants, citing release from jail as a study requirement. If study termination was required, the affected individuals would be notified by study staff. Of the 92-94% of participants who are released from jail to the community after the index incarceration, we conservatively estimate that post-release follow-up rates will be 82% at 4 weeks, 80% at 16 weeks, 75% at 34 weeks and 70% at 52 weeks, with 85% of participants providing data for at least one post-release follow-up interview. Post-release follow-up rates in previous and ongoing studies have been higher than this. Therefore, we expect that 78% (85%) of the 92% who are released from iail) of the 800 enrolled participants will provide evaluable follow-up data. Count (e.g., suicide events) data from missed follow-ups will be gathered at later follow-ups when they occur, and we will collect medical record and death record data on all eligible (i.e., released) participants.

Power. Our primary outcome (suicide events) is a composite of the number of suicide attempts (including suicide deaths), suicide behaviors (per the Columbia criteria), and suiciderelated hospitalizations. Previous trials of brief suicide risk reduction interventions in other at-risk populations have yielded relative risks of 1.6, 1.8, 57 1.8, 58 2.1, 59 and 2.6 60, 61 for suicide attempts  $(11.0 \text{ for suicide deaths}^{62})$ ,  $2.0^{60,61}$  and  $3.1^{209}$  for suicide behaviors, and  $1.8^{60,61}$  for hospitalization. This study is powered to detect an effect size at the lower end of the range of y/n effect sizes of successful similar studies, relative risk of 1.8 for any attempts, 2.0 for any behaviors, and 1.7 for any hospitalization (see below). In reality, our power will be better because we are measuring total number of each event, not just any event occurrence. Base rates. The literature provides information about base rates of suicide deaths among general populations of jail detainees, but not suicide events among jail detainees with suicide ideation. Therefore, we estimated control condition (base rate) event estimates among suicidal jail detainees conservatively as half the rates we observe in ED and inpatient studies. 57,60,61 This conservative estimate given our inclusion criteria of "yes" to C-SSRS item C4 or item C5 (some suicidal intent) or a suicide attempt in the month prior to enrollment is supported by rates of psychiatric observation (similar to inpatient hospitalization) for suicidality at jail entry (see D2.5). We express *clinical significance* using the area under the curve (AUC) statistic, following Kraemer. The AUC is flexible and has a direct and clinically relevant interpretation: the proportion of pairs, sampling one person exposed to the active treatment and another to the control, where the member of the pair exposed to SPI has a more favorable outcome profile. Our expected main effects translate into an AUC of 0.58, indicating that there is a 58% chance that a randomly selected participant from the SOC condition will have more suicide events than a randomly selected person from the SPI condition. This corresponds to a d=.28, meaning that our study is powered to detect small effects. This is the median effect size for suicide attempts reported in the literature, and we have super-adequate power to detect this effect (96.5%; see below). Estimation. We estimated power using Monte Carlo methods and 1001 replications per condition. Assuming: (1) the outcome is a total count of three outcomes [suicide attempts (including deaths), suicide behavior, and suicide related hospitalization] analyzed with ordinal logistic regression, (2) outcomes are correlated at 0.50 and have base rates of 10%, 18% and 12% in the control group and 5.5%, 9%, and 7% in the SPI group (where these percentages reflect cumulative annual incidence), and (3) a baseline sample of 800 released

persons of whom 78% are expected to provide evaluable data; using a type-I error risk of 5%, we will have 96.5% power to detect hypothesized main effects. Power is good but the study is not over-powered given the sensitivity of power to estimated effect sizes: assuming the control condition rates are as estimated, the minimum differences we can detect with 80% power would be SPI condition rates about 6.5% risk of attempts, 10.2% risk of behaviors, and 8% risk of hospitalization. The detectable effect size for *mediation* effects range from 0.11 to 0.13 as the correlation of the intervention and the potential mediator ranges from 0.2 to 0.5. Thus, we have power to detect any mediation effect that is clinically significant.

**Non-Completers and Non-Responders.** Given the unpredictable lives of our target group, flexibility is important in order to make the intervention accessible to them. Participants will *not* be discontinued from the intervention protocol for noncompliance because it has been our experience that recently incarcerated individuals can reengage with providers, even after a period of absenteeism. Participants who report significant suicide or homicidal risk, increased psychiatric symptoms or substance use will be referred to appropriate additional care, but will remain in the research protocol. All participants who are released from jail will be invited to continue all follow-up assessments, and research staff will attempt to maintain regular contact with all participants to collect data at each assessment interval.

and

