**Missing Data.** We will collect medical record and death record data on all participants. Self-reported count (e.g., suicide events) and historical (e.g., weekly LIFE ratings) data from missed assessments will be gathered at later follow-up assessments. We will use multiple imputation to deal with missing data. We will compare treatment conditions on rates of missingness and time to missingness and will test whether baseline characteristics are associated with missingness. Finally, we will perform a sensitivity analysis in which we impute extreme values for missing data to determine the sensitivity of analysis results to missing data.

**Outcomes.** Primary. We will test the hypothesis that, relative to SOC alone, SPI + SOC will result in fewer suicide events over the 52 week follow-up period, using ordinal logistic regression with lifetime suicide attempts events at baseline as a covariate. The analysis framework will be multivariate ordinal dependent variable regression. We begin with ordinal models because our simulations suggest the count outcome will not likely exceed 3. We will explore using different models such as zero-inflated Poisson or zero-inflated negative binomial with an offset defined by the length of follow-up and time in the community (as opposed to reincarcerated), and other reasonable approaches. Determination of the appropriate modeling will be determined using model selection (information) criteria and the determination will be made blind to the effect of the SIP intervention. Secondary. We will separately test the hypotheses that, relative to SOC alone, SPI + SOC will result in fewer suicide attempts, fewer weeks of active suicide ideation (per the LIFE calendar), lower severity of suicide ideation (C-

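### Section 10B's 58% chance that an SOC participant has more suicide events is impossible at the plan's own rates (at most 40%, about 25% on the simulated count), and AUC 0.58 does not follow at correlation 0.50

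*Combined protocol and SAP*

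**What the plan says.** All the figures are in the power text of section 10B. The AUC is introduced as a proportion of pairs, one member from each arm, "where the member of the pair exposed to SPI has a more favorable outcome profile". The plan continues: "Our expected main effects translate into an AUC of 0.58". It reads this as "there is a 58% chance that a randomly selected participant from the SOC condition will have more suicide events" than a randomly selected SPI participant, and equates it with d = .28.

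The assumptions follow in the same section. For the power simulation "the outcome is a total count of three outcomes" (attempts including deaths, behaviors, hospitalizations), analyzed by ordinal logistic regression. The "outcomes are correlated at 0.50 and have base rates of 10%, 18% and 12% in the control group", and 5.5%, 9% and 7% under SPI, "where these percentages reflect cumulative annual incidence". With 800 participants, 78% evaluable and a 5% type I error, "we will have 96.5% power to detect hypothesized main effects". The section also gives SPI rates of 6.5%, 10.2% and 8% as the smallest differences detectable with 80% power.

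Section 10A adds: "We begin with ordinal models because our simulations suggest the count outcome will not likely exceed 3". It lists the area under the curve among the clinical-significance measures to be reported for all major comparisons. Neither section mentions tied pairs or says on which scale the 0.50 correlation is defined.

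**The concern.** When most participants in both arms have no event, most random pairs tie. A statement that SOC has more events in 58% of pairs then looks too large, because a tied pair is not a pair in which SOC has more. The verbal reading appears to drop the tie term that an AUC normally carries, and the AUC may itself not match the assumed rates.

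What is at stake is interpretation. The figures 0.58 and .28 are the plan's benchmark for clinical significance, and an AUC is to be reported at the end of the trial. As written, a reader would believe that SOC does worse in most pairs. The reported AUC would also be compared with a benchmark that does not follow from the planning assumptions. No test, sample size or decision rule uses the AUC.

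**Working it through.** **Inputs** (section 10B unless noted). SOC rates 0.10, 0.18, 0.12; SPI rates 0.055, 0.09, 0.07; correlation 0.50, scale unstated; outcome the sum of three yes/no components; 0.78 × 800 = 624 evaluable, or 312 per arm at 1:1 (section 4A); two-sided 5% (section 10A).

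**1. The plan's power figure first.** The test was run in proportional-odds likelihood-ratio form (1001 simulations) and in its score (Wilcoxon) form (40,000 or more).
- Latent 0.50: 94.5% by likelihood ratio, 95.5% to 95.7% by score test. This approximately reproduces 96.5%.
- Phi 0.50: 92.5% to 92.9%. This does not reproduce it.

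The Monte Carlo standard error of 96.5% from 1001 replications is √(0.965 × 0.035 / 1001), or 0.6 points.

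**2. A cap that needs no model.** SOC more than SPI requires at least one SOC event, so

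P(SOC > SPI) ≤ P(SOC ≥ 1) ≤ 0.10 + 0.18 + 0.12 = 0.40.

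This holds at any correlation. The rates are any-event incidences, so it also holds however many events one person has. A value of 58% cannot occur.

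**3. The split on the 0-3 count.** Normal-threshold probabilities for counts 0/1/2/3:

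| Scale | SOC | SPI |
|---|---|---|
| Latent 0.50 | 0.717 / 0.189 / 0.070 / 0.023 | 0.836 / 0.122 / 0.034 / 0.009 |
| Phi 0.50 | 0.768 / 0.117 / 0.063 / 0.053 | 0.872 / 0.068 / 0.033 / 0.027 |

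At latent 0.50, from the unrounded probabilities:
- P(SOC > SPI) = 0.1893 × 0.8357 + 0.0702 × (0.8357 + 0.1222) + 0.0234 × (0.8357 + 0.1222 + 0.0335) = 0.249.
- P(tie) = 0.7170 × 0.8357 + 0.1893 × 0.1222 + 0.0702 × 0.0335 + 0.0234 × 0.0086 = 0.625.
- P(SOC < SPI) is the remainder, 0.126.

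**4. AUC with half credit for ties, and d.** AUC = P(SOC > SPI) + 0.5 × P(tie); d = √2 × z(AUC).

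| Correlation | SOC more | SOC fewer | Tie | AUC | d |
|---|---|---|---|---|---|
| Latent 0.50 | 24.9% | 12.6% | 62.5% | 0.561 | 0.22 |
| Phi 0.50 | 21.2% | 10.7% | 68.1% | 0.552 | 0.19 |
| Latent 0.20 | 27.6% | 13.4% | 59.1% | 0.571 | 0.25 |
| Zero | 28.9% | 13.4% | 57.6% | 0.577 | 0.28 |

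**5. Where 0.58 might come from.** The stated AUC and d agree with each other: Φ(0.28/√2) = 0.578. Two routes lead close to them.
- The half-tie AUC at zero correlation is 0.577 with d 0.276.
- A normal conversion of the mean-count difference at latent 0.50 works as follows. The means are 0.40 and 0.055 + 0.09 + 0.07 = 0.215, so (0.40 − 0.215)/0.636 = 0.29 and Φ(0.29/√2) = 0.58.

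The first contradicts the stated correlation. The second is not the proportion of pairs that section 10B defines.

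**6. The second power statement.** At SPI rates of 6.5%, 10.2% and 8% with 312 per arm, the score test has about 84% power at latent 0.50 and about 79% at phi 0.50, against the stated 80%. Latent fits the 96.5% better and phi fits the 80% better, so the scale cannot be inferred from the figures.

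**The case against.** The strongest defense is that the plan names an area under the curve, and the area under an empirical ROC curve already gives ties half credit. This largely stands. A reader might infer that, with no tie rule stated, the planned effect could be reported as 0.25 (ties as zero) or 0.66 (ties excluded). The documents do not support that. Scoring ties as zero would put two identical arms well below 0.5, and half credit is what the named statistic implies. The realistic gap is 0.58 against 0.56 or 0.55. The convention does not rescue the 58% sentence, which speaks of one arm having more events, and it does not give 0.58 at correlation 0.50.

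A second defense is that 0.50 is listed as an assumption of the power simulation, and the AUC may have been computed without it. That is possible, since zero correlation gives 0.577 and d 0.276. The origin of 0.58 is therefore unknown and should not be asserted. The plan nevertheless presents the AUC as the translation of its expected main effects, and under independence the simulated power would be about 99%, not 96.5%.

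Third, the trial counts total events, and section 10B notes that this is more informative than any-event indicators. Repeats would change the split, so the figures above describe only the simulated 0-3 count. They cannot rescue 58%. At latent 0.50, P(SOC ≥ 1) = 1 − 0.717 = 28.3% bounds the chance of more events whatever the repeats, and repeats matter only where both members have an event (0.283 × 0.164 = 4.6% of pairs).

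**Conclusion.** The statement is wrong as written; the error is minor. The 58% exceeds a cap of 40% that follows from the plan's incidences alone. On the simulated 0-3 count the chance is about 25% (latent 0.50) or 21% (phi 0.50), and 62% or 68% of pairs tie. With half credit for ties the AUC is about 0.56 (d about 0.22) or 0.55 (d about 0.19). Among the correlations examined, it rounds to 0.58 with d .28 only at zero, which contradicts the stated 0.50.

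The cap needs no assumption beyond the stated rates. The other figures assume a normal-threshold model for the three components and the 0-3 count.

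A reader might infer that the power calculation or the sample size fails. The documents do not support that: 96.5% is approximately reproduced on the latent scale, power is still about 93% on the phi scale, and the effect remains small in the plan's own terms. Nor can one conclude that the power text needs no attention if the scale was latent, because the 80% statement then comes out at about 84%.

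**What to change.** 1. In section 10B, replace the 58% sentence. For the latent reading: *On the simulated 0-3 count with latent correlation 0.50, an SOC participant has more events than an SPI participant in about 25% of random pairs, fewer in about 13%, and about 62% tie; counting ties as half, the AUC is about 0.56 (d about 0.22).* For the phi reading use 21%, 11%, 68%, 0.55 and 0.19.
2. State that ties count half, in section 10B and for the AUC reported under section 10A.
3. State whether 0.50 is a latent or an observed binary (phi) correlation.
4. Check both power statements on that scale and restate whichever does not reproduce. For the 96.5%, expect about 96% latent or 93% phi. For the 80% minimum-detectable rates, expect about 84% latent or 79% phi.

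The cost is a few lines of text and, at most, a rerun of the existing simulation. Sample size, test and decision rule stay as they are.

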## 10. Statistical Analysis

## 10A. Data Analysis

Primary analyses will be *intent-to-treat;* we will examine dose-response effects in secondary analyses. Primary tests will be 2-sided with  $\alpha$ =0.05. Site differences will be modeled with fixed effects. Descriptive statistics will include effect sizes and measures of clinical significance (i.e., area under the curve; number needed to treat) for all major comparisons. We will separate primary hypothesis (Aim 1) from remaining hypotheses (Aims 2-4). Standard post hoc procedures will be used to adjust for multiple comparisons when testing secondary hypotheses. There is no planned interim analysis. Analyses will adjust for baseline levels of dependent variables, gender, and yes/no history of suicide attempts. Consistent with CONSORT guidelines, we will pre-specify covariates and will not adjust for imbalance observed post hoc.

The original grant application stated that: "We will finalize and total data from each study phase that has been completed as they are completed (i.e., intake and 1-month follow-up will be complete by Month 32, 4-month follow-up will be complete by Month 35, 8-month follow-up will be complete by Month 39, and 12-month will be complete by Month 43). Given the timelines for data cleaning and recoding described above, intake and 1-month follow-up data will be available for analysis by Month 32, 4-month follow-up will be available for analysis by Month 35, 8-month follow-up data will be available for analysis by Month 39, and 12-month data will be available for analysis by the end of Month 43." Our timeline slid a little from this proposal due to recruiting another 3 months and waiting to see if anyone else would get out of jail. At this point, per the original analysis plan, we will close the assessment windows and begin data analysis for each wave as follows:

- Baseline: 4/12/19
- 4-week: 4/12/19 (all participants will be at least 4-weeks from their release date at this point)
- 16-week: 5/12/19 (all participants will be at least 16-weeks from their release date by this date)
- 34-week: 9/12/19 (all participants will be at least 34-weeks from their release date by this date)
- 52-week: 1/20/20 (all participants will be 52-weeks from their release date by this date)

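### The 96.5% power assumes a full-year count for everyone with one interview, and the plan does not say how an incomplete year's count enters the primary ordinal analysis

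*Combined protocol and SAP*

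**What the plan says.** All references are to the combined protocol and SAP.

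- **Power (10B).** The inputs for the three components are given as follows: "outcomes are correlated at 0.50 and have base rates of 10%, 18% and 12% in the control group and 5.5%, 9%, and 7" (the last three figures, in per cent, belong to SPI). A bracketed note makes clear that they are annual: "where these percentages reflect cumulative annual incidence". With 800 "persons of whom 78% are expected to provide evaluable data", the conclusion is that "we will have 96.5% power to detect hypothesized main effects". No partial follow-up is described.
- **Attrition (10B, also 3A).** Of those consented, 92–94% are released. For those released, the two later follow-up rates and the share with any interview are stated as "75% at 34 weeks and 70% at 52 weeks, with 85% of participants providing data for at least one post-release follow-up interview". The two earlier rates are 82% (week 4) and 80% (week 16). The 78% is the product of 85% and 92%.
- **Primary model (10A, Outcomes).** Total events over 52 weeks are analysed "using ordinal logistic regression with lifetime suicide attempts events at baseline as a covariate". An offset for observed time and time out of custody is attached to the zero-inflated alternatives and to the secondary count outcomes. None is attached to the ordinal model.
- **Incomplete data (10A, Missing Data; 9; 10B).** Missed counts are collected at a later interview if one takes place. Hospital and death records are sought for everyone released. Multiple imputation is planned, with an extreme-value sensitivity analysis and a comparison of missingness by arm.

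**The concern.** The primary outcome is a 52-week total. Catching up at a later interview closes gaps between interviews, but not the time after a person's last one. The power simulation nevertheless gives every evaluable person a whole year of risk.

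The analysis side has the matching gap. Section 9 builds the total from interviews, charts and registries together. Someone last interviewed at week 4 with nothing in the records therefore has a total of zero. That total is not blank, so nothing marks it as incomplete and in need of imputation, and the ordinal model has no term that would allow for the shorter observation.

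Two things are at stake: a few points of stated power, and the protection of the primary estimate if follow-up differs by arm. SPI participants receive at least four planned clinician calls over six months (1H) and SOC participants do not, so equal retention cannot be taken for granted. Preparatory, aborted and interrupted acts carry the highest assumed rate (18% v 9%). They may never reach a hospital, and then they depend on interviews.

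**Working it through.** **Who is followed for how long** (rates from 10B)

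- Released: 800 × 0.92 = 736.
- Evaluable: 736 × 0.85 = 625.6, about 626. The plan's rounded 78% gives 624, or 312 per arm at 1:1.
- With a 52-week interview: 736 × 0.70 = 515.2, about 515, which is 64.4% of 800.
- Evaluable but last interviewed earlier: 626 − 515, about 110.

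**Bounds on the last interview.** Per 85 evaluable people, 70 are seen at week 52. At least 75 have their last interview at week 34 or later, and at least 80 at week 16 or later. The least favourable mix is therefore 70/5/5/5 at weeks 52/34/16/4. The most favourable is 70 at week 52 and 15 at week 34. Mean share of the year covered:

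- Most favourable: (70 + 15 × 34/52)/85 = 0.939.
- Least favourable: (70 + 5 × (34 + 16 + 4)/52)/85 = 0.885.

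**Reproducing 96.5%.** Three correlated yes/no events were summed to 0–3, with 312 per arm, two-sided 0.05 ("Primary tests will be 2-sided with" α = 0.05 in 10A) and full-year data for all. The proportional-odds likelihood-ratio test gave 96.1% (1001 replications), and the tie-corrected rank-sum test, its near-equivalent, gave 95.7–95.8%. The simulation error of the plan's own figure is √(0.965 × 0.035/1001) = 0.6 points, so this agrees. It requires reading the 0.50 as a latent correlation. Read as a phi coefficient, it gives about 92–93% and does not reproduce the plan.

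**Same simulation with the plan's follow-up** (rank-sum test, latent 0.50, equal dropout)

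| Scenario | Power |
|---|---|
| Full year for all 624 | 95.8% |
| Events after last interview lost, uniform timing | 94.8% to 93.1% (most to least favourable mix) |
| Same, events front-loaded | 95.3% to 94.2% |
| Hospitalizations recovered from records, uniform timing | 95.1% to 94.1% |
| Hospitalizations plus 43% of other lost events recovered, uniform timing | 95.6% to 95.1% |
| 52-week completers only, 258 per arm | 91.5–92% |

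The 43% borrows the chart-review yield quoted in section 9 and is an assumption here. If records supplied attempts and hospitalizations for everyone released, power would reach about 96%. Under the phi reading the corresponding figures are 92.9% (full), 91.7% to 89.5% (events after last interview lost) and 87.5% (completers).

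**Unequal retention, illustration only.** Assume 52-week retention of 75% SPI v 65% SOC, 85% with any interview in both arms, uniform timing, and partial counts used as they stand. The true ratio of expected totals is (5.5 + 9 + 7)/(10 + 18 + 12) = 21.5/40 = 0.54.

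- Least favourable mix. Shares covered: SPI (75 + 10/3 × 54/52)/85 = 0.923; SOC (65 + 20/3 × 54/52)/85 = 0.846. Apparent ratio: 0.5375 × 0.923/0.846 = 0.59.
- Same mix, hospitalizations recovered: (14.5 × 0.923 + 7)/(28 × 0.846 + 12) = 20.4/35.7 = 0.57.
- Most favourable mix. Shares covered: 0.959 and 0.919. Apparent ratio: 0.56, or 0.55 with hospitalizations recovered.
- Retention reversed, least favourable mix: 0.5375 × 0.846/0.923 = 0.49, which exaggerates the benefit.

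In the 0.59 case, simulated power fell to about 83–84%.

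**The case against.** The sponsor can fairly say that the plan is not silent on missing data. It names multiple imputation, a sensitivity analysis, catch-up at later interviews and record searches, and section 8D keeps those lost to follow-up in the analysis. The ordinal model may also give way, through model selection blind to the intervention effect, to a count model that has an offset. The follow-up rates are called conservative, the base rates are set at half those seen in emergency and inpatient studies, and power on 624 ignores any record data from the other 110 or so released people. Follow-up is done by assessors blind to arm, not by the SPI clinicians. All of this stands, and it keeps the power effect small.

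It also rules out four stronger readings that a reader might infer:

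- *Short follow-up is scored as event-free.* No section says so, and the imputation and record provisions point the other way. What is missing is a rule, in either direction.
- *True power is about 92%.* That is the completers-only floor, not the expected value.
- *Bias will be toward the null.* The documents predict no difference in retention; the 75% v 65% split is invented for illustration, and the reverse split biases the other way.
- *Describing the 800 as released inflates the sample.* It is a wording slip: 800 is the enrolled number, but 78% already contains the release factor, so 624 is unaffected.

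The provisions do not answer the remaining question. Imputation acts only on values recognised as missing, and a total assembled from several sources looks complete.

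**Conclusion.** The point holds in a limited form. The 96.5% is correct arithmetic for full-year data on 624 people, which the plan's own follow-up rates do not deliver. Truncation costs about 1 to 3 points, and using completers only costs about 4. This rests on latent correlation 0.50, equal dropout, uniform event timing, no covariates, and a last-interview mix bounded by the plan's rates. Every equal-dropout scenario stays above 87%, even under the phi reading, so the sample size is not undermined.

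The more important finding is the unspecified handling of an incomplete year in the primary analysis. Its effect on the estimate cannot be predicted from the documents. The illustration shows that a 10-point retention gap could move the event ratio by up to about 0.05 in either direction if partial counts were used unadjusted.

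**What to change.** 1. **Power (10B).** Repeat the simulation with the 82/80/75/70% follow-up pattern. Report about 93–95%, with the range 92–96%, and state the type of correlation, the event timing and the degree of record recovery assumed. Correct the description of the 800 from released to enrolled.
2. **Primary analysis (10A).** Run the planned multiple imputation by interview interval: 0–4, 4–16, 16–34 and 34–52 weeks. Treat an interval's self-report as observed if that interview, or a later one covering it, was completed; otherwise treat it as missing. Keep record-detected events in missed intervals as observed. Sum the intervals to a 52-week count in each imputed data set before fitting the ordinal model. State that a partial count is never entered as a full-year count.

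The cost is SAP wording, some imputation programming, one repeat of the simulation and a slightly lower stated power. Design, sample size and data collection do not change.
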